**Table 10-1 Lower Exact 90% Two-Tailed Confidence Limits for Selected Objective Response Rate Results for 25 Subjects**

Number of Responses	Response Rate	Lower Confidence Limit
1	4.0%	0.2%
2	8.0%	1.4%
3	12.0%	3.4%
4	16.0%	5.7%

The final decision to pursue the clinical development of any disease-specific cohort will be based on safety evaluations, the complete results of the study, and other factors; fewer than 3 responses could be considered a discouraging result. When 3 or more responses are observed, there is approximately a 75% probability this occurs when the true rate is 15%, but less than 13% when the true rate is 5%. When 4 responses are observed, a 5% rate is excluded by the 90% confidence interval (CI) lower bound.

An interim futility analysis is planned for each cohort, which may have an impact on the number of subjects ultimately enrolled in Part B. The futility analysis is described in [Section 10.3.6](#).

- The Other NEC/NET and Other Solid Tumor cohorts will enroll subjects until all other disease cohorts complete enrollment, and are expected to enroll approximately 30 subjects each by the time of study completion.
- Details will be provided in the SAP.

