### **Part B Expansion Cohorts**

To explore the recommended dosing regimen for distinct disease subsets, subjects will be enrolled in disease-specific expansion cohorts in Part B. The dose regimen(s) to be examined in the disease-specific cohorts will be at the MTD determined in Part A or a lower dose(s) and/or regimen(s), depending on the cumulative data. For example, a lower dose regimen may consist of a finite number of doses and/or a mixed-dose regimen, with all doses at or below MTD, but varying based on the cycle. The dose(s), regimen(s), and schedule(s) for the expansion cohorts will be determined by the Sponsor in consultation with the SMC.

In Part B, up to approximately 174 subjects may be enrolled, including approximately 19 subjects in each of the 5 disease-specific cohorts and up to 30 subjects each for Cohort 7 and Cohort 8. The goal of the Part B expansion is to provide further safety data and preliminary efficacy data for the selected dose regimens.

Response will be assessed by radiographic imaging at protocol-specified time points determined by the subject's dosing schedule. In the 6-week cycle schedule, tumor response will be assessed every 6 weeks during active study treatment until 24 weeks, then every 12 weeks, thereafter. Prostate cancer-specific assessments are described in [Appendix 13.6](#).

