### 3. Investigational Plan

#### 3.1 Summary of Study Design

This is a multicenter, open-label study of rovalpituzumab tesirine in subjects with DLL3-expressing advanced solid tumors. The study will include 7 cohorts of subjects with the following cancers:

1. Malignant melanoma
2. Medullary thyroid cancer (MTC)
3. Glioblastoma
4. Large cell neuroendocrine carcinoma (LCNEC) of any origin
5. Neuroendocrine prostate cancer (NEPC)
6. High-grade gastroenteropancreatic neuroendocrine carcinoma (GEP NEC)
7. Other neuroendocrine carcinoma (NEC) and high grade neuroendocrine tumors (NET)
8. Solid tumors other than the above

As of protocol version 4.0, cohort 3 (Glioblastoma) is closed to enrollment. Specific guidance for cohort 3 (Glioblastoma) subjects (protocol version 3.0) are provided in Appendix 13.3.

Each disease-specific cohort will include two parts:

- Part A – Dose-Regimen Finding: Will involve disease-specific dose escalation, and possible dose-interval modification, to define the maximum tolerated dose (MTD) and/or possible recommended Phase 2 dose(s) (RP2Ds).
- Part B – Expansion Cohorts: Disease-specific expansion cohorts may be enrolled. Subjects in the expansion cohorts will be treated with a dose regimen(s) at or below the MTD and/or RP2D determined in Part A.

Dose limiting toxicities (DLTs) will be assessed during the DLT Evaluation Period (Section 3.1.3) for subjects in Part A, the dose regimen finding portion of the trial.

Safety will be monitored throughout the trial by the Safety Monitoring Committee (SMC) consisting at least of a Medical Monitor, Investigators, and the study biostatistician. The SMC will meet routinely to review the emerging safety, select pharmacodynamic and efficacy data, and may make dose-escalation and dosing-interval recommendations. The SMC may recommend further evaluation of safety at a given dose level, investigation of alternative dose regimens, including a dose level that is intermediate to the planned dose levels, modification of the dosing interval, limitation to the maximum number of doses, and/or elimination or cancellation of a dose level(s) in a cohort based on the experience in other cohorts. The SMC will also review cumulative safety data in order to identify safety concerns that may emerge due to cumulative exposure beyond the DLT window. The process for dose-escalation decisions and dose-interval recommendations, and the roles and responsibilities of the SMC may be detailed separately.

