### 10.1 Determination of Sample Size

Up to approximately 318 subjects are expected to participate in this two-part trial.

In Part A, up to approximately 144 subjects may be enrolled, assuming 3 dose-escalation cohorts of 6 subjects each (18 subjects) across 8 disease cohorts. The exact number will depend on the number of cohorts required to reach the MTD in each disease, and the number of subjects enrolled in each disease-specific cohort.

In Part B, up to approximately 174 subjects may be enrolled, including approximately 19 subjects in each of the 5 disease-specific cohorts. The rationale for the sample size is based on the assumption that an ORR of around 15% would be indicative of efficacy worthy of further investigation given the advanced cancers and extensive treatment history in this study population. Additionally, an ORR below 5% would provide evidence of an ineffective treatment. The goal of the efficacy analyses is to provide a preliminary signal that the response rate may potentially be within that target range.

When Part B is enrolled, each disease-specific cohort will have approximately 25 subjects treated at the RP2D, including the Part A and Part B subjects. [Table 10-1](#) presents the 90% two-tailed lower exact confidence limits for selected response rates.

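### The response benchmark in Section 10.1 is worked out for 25 subjects only; at the roughly 30 expected in Cohorts 7 and 8 its printed probabilities and its 4-response statement do not hold

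*Combined protocol and SAP*

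**What the plan says.** Section 10.1 takes an ORR of about 15% as worth pursuing and one below 5% as showing no efficacy. It plans that "each disease-specific cohort will have approximately 25 subjects treated at the RP2D, including the Part A and Part B subjects", and Table 10-1 lists exact lower 90% limits for that size. The paragraph under the table addresses the decision on any disease-specific cohort. It says that "fewer than 3 responses could be considered a discouraging result", puts the chance of 3 or more responses at about 75% for a true rate of 15% and below 13% for 5%, and adds: "When 4 responses are observed, a 5% rate is excluded by the 90% confidence interval (CI) lower bound".

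Cohort 7 (other neuroendocrine carcinoma and high-grade tumors) and Cohort 8 (other solid tumors) are sized differently. Section 10.1 says that they "will enroll subjects until all other disease cohorts complete enrollment" and "are expected to enroll approximately 30 subjects each by the time of study completion". The synopsis, under Part B Expansion Cohorts, gives "up to 30 subjects each for Cohort 7 and Cohort 8". No response count, probability or confidence limit is given for any final cohort size other than 25; Section 10.1 says only that details will follow in the SAP.

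**The concern.** A fixed response count does not keep its properties as n grows. With more subjects, 3 responses are easier to reach by chance at a 5% rate, and 4 responses are a smaller proportion with a lower confidence limit. A reader who applies the printed benchmark to a cohort of 30 would therefore believe that it screens out a 5% response rate better than it does, and that 4 responses rule out 5% when they do not.

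The document invites that reading. Section 3.1 lists all the cohorts, 7 and 8 included, and then says "Each disease-specific cohort will include two parts". The Part A paragraph of Section 10.1 counts 8 disease cohorts and goes on to use the disease-specific label for each. Cohorts 7 and 8 are the two largest expansion cohorts, 2 × 30 = 60 Part B subjects between them.

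**Working it through.** **Inputs.** ORR of 5% and 15%, response counts of 3 and 4, and exact two-tailed 90% limits (5% in each tail): Section 10.1. n = 25: Section 10.1. n = 30: Section 10.1 and the synopsis. n = 36 is an assumption: 30 from Part B plus the 6 subjects that Section 3.1.1 requires as a minimum at the maximum tolerated or recommended dose, by analogy with 19 + 6 = 25.

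**Formulas.** P(X ≥ 3) = 1 − P(0) − P(1) − P(2), with X binomial(n, p). The exact lower limit for x responses is the 5% quantile of Beta(x, n − x + 1). Equivalently, x responses exclude 5% when P(X ≥ x) at p = 0.05 is below 0.05.

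**The plan's own figures, n = 25.**
- ORR 5%: 1 − 0.2774 − 0.3650 − 0.2305 = 0.127, which agrees with the stated bound of 13%.
- ORR 15%: 1 − 0.0172 − 0.0759 − 0.1607 = 0.746, which agrees with about 75%.
- Lower limit for 4/25: 5.66%, which agrees with the 5.7% in Table 10-1.

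**The same calculation at n = 30.**
- ORR 5%: 1 − 0.2146 − 0.3389 − 0.2586 = 0.188.
- ORR 15%: 1 − 0.0076 − 0.0404 − 0.1034 = 0.849.
- Lower limit for 4/30: 4.69%. Cross-check: P(X ≥ 4) at 5% is 0.061, above 0.05, so 5% is not excluded.
- Lower limit for 5/30: 6.81%. Cross-check: P(X ≥ 5) at 5% is 0.016, so 5% is excluded.

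| | n = 25 | n = 30 | n = 36 (assumed pooling) |
|---|---|---|---|
| P(≥3), ORR 5% | 12.7% | 18.8% | 26.8% |
| P(≥3), ORR 15% | 74.6% | 84.9% | 92.2% |
| P(≥4), ORR 5% | 3.4% | 6.1% | 10.4% |
| P(≥4), ORR 15% | 52.9% | 67.8% | 80.9% |
| Lower 90% limit, 4 responses | 5.7% | 4.7% | 3.9% |
| Lower 90% limit, 5 responses | 8.2% | 6.8% | 5.6% |

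**Where the statements stop holding.** The 13% bound is passed at n = 26 (13.9%). Four responses exclude 5% up to n = 28 (limit 5.03%) but not at n = 29 (4.85%).

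**Effect of the futility look.** Section 10.3.6 plans a non-binding look at 12 subjects. Suppose that enrollment always stopped at 0 of 12. At ORR 5%, P(0 of 12) = 0.540. The paths lost are those with 0 of 12 followed by at least 3 among the remaining 18, for which P = 0.058. So 0.188 − 0.540 × 0.058 = 0.156 at n = 30. At n = 36 the remaining 24 give P = 0.116, and 0.268 − 0.540 × 0.116 = 0.205. Both are still above 13%.

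**The case against.** The strongest objection concerns scope. Section 10.1 also uses the term narrowly: its Part B paragraph has an enrollment "including approximately 19 subjects in each of the 5 disease-specific cohorts", the synopsis sets those five apart from Cohorts 7 and 8, and the sentence giving about 25 per cohort can describe only the five. Table 10-1 names 25 subjects in its title, and Cohorts 7 and 8 have their own bullet. On that reading nothing printed is false. This stands in part: the plan has no arithmetic error, and its scope is ambiguous rather than plainly wrong. But the narrow reading leaves the two largest expansion cohorts with no efficacy benchmark, so the text needs the same addition either way.

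A reader might also infer that 3 responses is a go rule and that 19% to 27% is its false-positive rate. The documents do not support that. Having fewer than 3 responses only could be seen as discouraging, the decision also rests on safety, the complete results and other factors, and 3 or more is never called sufficient. Section 10.3.4 reports each cohort's response rate with its own 90% interval, so a result of 4/30 would appear with its correct limit.

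Nor should 27% be read as the plan's figure. Pooling is stated only for the cohorts reaching about 25, and about 30 by study completion can be read as a total.

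Finally, the SAP to which Section 10.1 defers is not in the text available for this review, so a size-specific rule there cannot be excluded. Section 10.1 would still carry unqualified statements.

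**Conclusion.** The point holds as a gap in scope and missing operating characteristics, not as a miscalculation. At the plan's own expected size of about 30, with no pooling assumed, the chance of 3 or more responses at a 5% response rate is 18.8% rather than below 13% (15.6% if a 0-of-12 stop were always followed), and 4 responses do not exclude 5%; 5 are needed. At n = 36 the first figure is 26.8% (20.5% with the stop), conditional on pooling six Part A subjects. These are chances of reaching a soft benchmark, not formal type I error rates. It would be going too far to conclude that the plan sets a lax decision rule for these cohorts or that inactive settings will be carried forward because of it. The correction should be made, because the printed probabilities are what a reader would use to interpret the response count.

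**What to change.** In Section 10.1:

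1. Limit the 3-response and 4-response statements, with their probabilities, to cohorts of about 25 subjects.
2. Add the probabilities and lower confidence limits for Cohorts 7 and 8 at n = 30, and at n = 36 if Part A subjects will be pooled, and state that 5 responses are needed to exclude 5% at either size. Say explicitly whether 30 is a Part B number or a total.
3. Because enrollment in these cohorts runs until the others finish, give the benchmark by the n actually reached, for example as a short table.

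The discouraging threshold for these cohorts is the sponsor's choice. At n = 30, keeping 3 gives 18.8% at ORR 5% and 84.9% at ORR 15%; moving to 4 gives 6.1% and 67.8%. The stricter threshold costs 84.9 − 67.8 = 17.1 percentage points at the target rate and falls below the plan's own 75%, so neither is clearly better. Whichever is kept, its true probabilities should be printed.

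The cost is a few sentences and a small table, with no change to enrollment, data collection or the planned analyses.

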## 10.2 Analysis Populations

The following populations will be considered:

- Full Analysis Set: All enrolled subjects who receive any amount of study drug.
- Safety Set: All subjects who receive any amount of study drug and have at least one post-baseline safety evaluation.
- DLT-Evaluable Set: All subjects who receive any amount of study drug and either experienced a DLT or were followed for the full DLT evaluation period.
- Pharmacokinetic-Evaluable Set: All subjects who receive at least 1 dose of study drug and for whom a baseline measurement and at least one blood sample following a dose of study treatment are available.

Based on the actual deviations, the criteria for exclusion of subjects from the different data sets will be specified and updated, if necessary, prior to database lock.

## 10.3 Planned Analyses

As a general strategy, continuous efficacy and safety endpoints will be summarized using the five-number summary (mean, standard deviation, median, minimum, and maximum). Frequency distributions (counts and percentages) will be used to summarize categorical endpoints.

### 10.3.1 Disposition of the Study Subjects

The disposition of subjects will be described with summaries by disease and cohort of the number of subjects enrolled, the number of subjects treated, the number of subjects for whom study drug was permanently discontinued (including the reasons for discontinuation), and the number of subjects who discontinued early from the study.

### 10.3.2 Demographic and Baseline Characteristics

Demographic and baseline characteristics will be summarized and compared by disease and cohort. Results will be reported using subjects in the full analysis set.

### 10.3.3 Exposure to Study Treatment and Compliance

Frequency distributions of the number of received doses will be presented by disease and cohort. Treatment duration and treatment compliance for all randomized subjects will be described by

disease and cohort.

#### **10.3.4 Analysis of Primary Efficacy Endpoints**

The first primary efficacy endpoints are the best objective response rate based on RECIST v1.1 and/or, for prostate cancer subjects, PCWG3 criteria. It is defined as the proportion of subjects whose best overall response is either CR or PR according to RECIST v1.1 or PCWG3. The best overall response is the highest recorded response through End of Treatment. The number and percentage of responders along with the corresponding 90% two-tailed CI will be provided for each disease and cohort.

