In a Phase 2 SCR001-002 (TRINITY) study in patients with SCLC recurrent after at least two systemic chemotherapy regimens, rovalpituzumab tesirine dosed at 0.3 mg/kg every 6 weeks for two cycles (with an option for additional two cycles upon progression occurring  $\geq 12$  weeks after the second dose) had shown confirmed objective response rate of 16%, progression-free survival of 3.9 months and overall survival of 5.6 months in 3rd line DLL3High patients. Of note, prolonged stable disease with target lesion size reduction has been observed in a considerable number of patients receiving additional post-progression cycles of rovalpituzumab tesirine. Drug related grade 3 or above treatment emergent adverse events that occurred in at least 10 subjects include thrombocytopenia (11%), photosensitivity reactions (7%), anemia (4%), fatigue (4%),

and pleural effusion (4%). Adverse events leading to study treatment discontinuation occurred in 7% of subjects (AbbVie Stemcentrx, data on file).

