### **7.3 Radiographic Response/Efficacy Assessments**

Radiographic evaluations at protocol-specified time points include:

- CT scans of the chest, abdomen and pelvis (scans of the neck must also be obtained for MTC and/or if there is documented or suspected involvement in this region)
- MRI of the brain, if indicated. CT of the brain with intravenous contrast may be substituted at the discretion of the Investigator.
- Whole-body technetium-99m (99mTc) bone scintigraphy (prostate cancer subjects only)

Diagnostic quality, spiral CT scans are recommended; other methods may be used if performed consistently throughout the study for each individual subject. Positron emission tomography (PET) and/or octreotide/somatostatin scans may be used in an ancillary manner; however, no decisions relating to PD may be made based on PET or octreotide/somatostatin scans alone. Clinical response will be determined by the Investigator at each assessment according to RECIST v1.1 ([Appendix 13.6](#); [Eisenhauer 2009](#)), and/or for prostate cancer subjects, PCWG3 criteria ([Appendix 13.7](#)).

For tumors to be assigned a status of responder (PR or CR), changes in tumor measurements must be confirmed by repeat assessments performed no less than 4 weeks, but preferably not more than 6 weeks, after the criteria for response are first met; i.e., two consecutive assessments of PR or CR are required. In instances where a follow-up visit is not otherwise scheduled to occur for more than 6 weeks, repeat radiographic disease assessments should be conducted at least 4 but not more than 6 weeks after the criteria for response are first met, in order to confirm response, whether or not a formal follow-up visit is conducted at the same time.

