- 15) Urinalysis includes dipstick results for color, appearance, specific gravity, pH, glucose, bilirubin, ketones, occult blood, and protein; as well as spot analysis of protein and creatinine for ratio.
- 16) Hepatitis B and C tests include HBsAg, HBsAb, HBcAb and HCV antibody. Results that may be consistent with chronic or active infection must be confirmed by PCR tests for Hep B and/or C.
- 17) Pregnancy test consists of blood or urine testing for  $\beta$ -hCG in women of child-bearing potential. Repeat testing may be done as requested by the Investigator.

- 18) ECG consists of a 12-lead study. ECGs will be done in triplicate at the indicated times.
- 19) ECHO includes assessment of left LVEF and pericardial effusion. The screening ECHO should be done any time before the first dose of study drug, either during screening or pre-dose on CID1; all ECHOs after CID1 should be conducted within 4 days before the next dosing.
- 20) Fluid Retention Questionnaire includes queries of daily weights and worsening or new edema or dyspnea.
- 21) Subjects will maintain a diary of daily weights.
- 22) Concomitant medications include names of all concomitant therapies, including dates of administration, dose regimen, route of administration, and purpose
- 23) CT imaging of the chest, abdomen, and pelvis, and neck (if indicated) for all subjects, for assessment via RECIST v1.1. Subjects who achieve a partial or complete response must undergo confirmatory assessment(s) as described in [Section 7.3](#).
- 24) Standard of Care procedures completed prior to the subject signing ICF, but within the study screening window, may be used as screening procedures.
- 25) CT of the brain with intravenous contrast may be substituted at the discretion of the Investigator.
- 26) MRI of the brain is only required after screening when clinically indicated (e.g., if CNS progression is documented).
- 27) PRO assessments (questionnaires) are required for subjects in Part B of the study (only) at screening, and also on Cycle 2 Day 1, Cycle 2 Day 29, and EOT.
- 28) Tumor tissue assessment consists of procurement for DLL3 testing of archived, representative tumor tissue, or an optional fresh tumor biopsy, if accessible. With consent from the subject, tumor tissue may be obtained prior to the screening period and tested for DLL3 expression. Optional: collection of tumor tissue at progression to better understand mechanisms of resistance and expression of DLL3.

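### Sections 7.3 and 10.3.4 give conflicting rules for who counts as a responder, and nothing says which one governs the ORR, DOR and the 3-of-25 guide

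*Combined protocol and SAP*

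**What the plan says.** Section 10.3.4 defines the response rate: "It is defined as the proportion of subjects whose best overall response is either CR or PR according to RECIST v1.1 or PCWG3". It adds: "The best overall response is the highest recorded response through End of Treatment". It does not mention confirmation or refer to Section 7.3. The RECIST table in Appendix 13.6 has no confirmation rule either.

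Section 7.3 has the Investigator determine response at each assessment, then restricts the status: "For tumors to be assigned a status of responder (PR or CR), changes in tumor measurements must be confirmed by repeat assessments". The repeat must come no less than 4 weeks later, and "two consecutive assessments of PR or CR are required". Footnote 23 of the Schedule of Assessments makes the repeat scan mandatory: "Subjects who achieve a partial or complete response must undergo confirmatory assessment(s) as described in" Section 7.3. It does not say how a response that fails confirmation, or is never rescanned, is to be counted.

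Section 10.3.5 summarises DOR for responders, described there only as subjects with CR or PR. Section 10.1 names ORRs of 5% and 15% as the uninteresting and interesting rates, without saying whether they are confirmed. For about 25 subjects per disease-specific cohort it offers a soft guide: "fewer than 3 responses could be considered a discouraging result".

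**The concern.** The two sections classify the same subject differently. Someone with a PR at week 6 and stable disease at week 12 has a highest recorded response of PR, so is a responder under Section 10.3.4 as written. Under Section 7.3 that subject is not. Two programmers working from this text could report different ORRs and different DOR populations from the same data.

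The cut-off at End of Treatment adds a second difficulty. Section 6.4 places that visit about 42 days after the last dose, or within 7 days of the decision to stop if that is later. Section 3.1.2 allows regimens with a finite number of doses, and Section 6.5 continues scans in follow-up. A PR first seen near End of Treatment may therefore be confirmed only after the cut-off. Even a reader who assumes a confirmed ORR cannot tell how to count that subject.

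Efficacy in each cohort is read from a handful of responses, assessed by the Investigator in an open-label study, so a difference of one or two subjects is visible in the result.

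**Working it through.** **Inputs from the documents.** n = 25 per disease-specific cohort, benchmark rates 5% and 15%, guide of 3 or more responses, and the remark about 4 responses (all Section 10.1 and Table 10-1); interim look at 12 subjects (Section 10.3.6).

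**Input not in the documents.** The share u of recorded responses that are never confirmed. It is an assumption, shown from 10% to 50%.

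**Step 1: reproduce the plan's figures.** P(X ≥ 3) = 1 − Σ C(25,k) p^k (1−p)^(25−k), for k = 0, 1, 2.

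- p = 0.05: 1 − (0.2774 + 0.3650 + 0.2305) = 0.1271, or 12.7% (plan: less than 13%).
- p = 0.15: 74.6% (plan: about 75%).

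The exact lower 90% two-sided limit for x of 25 is the 5th percentile of Beta(x, 26 − x):

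- x = 4: 5.66%, shown as 5.7% in Table 10-1.
- x = 3: 3.35%, shown as 3.4%.

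**Step 2: one reclassified subject.** If one of four recorded responses is unconfirmed, the count is 4/25 under the literal Section 10.3.4 rule and 3/25 under Section 7.3. The first excludes 5% and the second does not. This needs no value for u, but it also says nothing about how likely the event is.

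**Step 3: the effect if 5% is a confirmed rate.** Hold the confirmed ORR at 5%. The recorded rate is then 0.05/(1 − u). For u = 10% it is 0.0556, and P(X ≥ 3) = 1 − (0.23956 + 0.35229 + 0.24868) = 0.1595 (15.9% from the unrounded value, 0.15948).

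| Assumed u | Recorded rate | P(≥3 of 25) | P(≥4 of 25) | Interim P(≥1 of 12) |
|---|---|---|---|---|
| 0% | 5.0% | 12.7% | 3.4% | 46.0% |
| 10% | 5.6% | 15.9% | 4.7% | 49.6% |
| 20% | 6.3% | 20.3% | 6.7% | 53.9% |
| 30% | 7.1% | 26.3% | 9.9% | 58.9% |
| 40% | 8.3% | 34.7% | 15.0% | 64.8% |
| 50% | 10.0% | 46.3% | 23.6% | 71.8% |

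**Step 4: the other mismatch.** If 15% was meant as a recorded rate and only confirmed responses are counted, P(≥3 of 25) falls from 74.6% to 67.5%, 59.1% or 28.8% when 90%, 80% or 50% of responses confirm (rates 13.5%, 12% and 7.5%). If benchmark and count use the same definition, whichever it is, the plan's 12.7% and 74.6% apply unchanged.

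**The case against.** The strongest reply is that the sections can be read together. Section 7.3 says when responder status may be assigned, and Section 10.3.4 reports the number and percentage of responders, so the counted status may simply be the confirmed one. The mandatory confirmatory scan, and the interim's requirement of at least 2 evaluable assessments, are compatible with that. This stands as a possible reading, so a reader should not infer that the plan has settled on an unconfirmed ORR. It does not remove the conflict. Section 10.3.4 gives its own rule for best overall response, Section 10.3.5 describes responders without confirmation, and neither reading settles the End of Treatment cut-off.

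A reader might also infer that the false-signal rate is raised outright. The documents do not support that: they never label 5% and 15% as confirmed, and they give no unconfirmed share.

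Nor does the 3-response count decide development. Section 10.1 words it as guidance, and rests the decision on safety, the complete results and other factors. Antitumor activity is a secondary objective.

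It is also tempting to say that the ORR would not be comparable with the confirmed SCLC rates of 31% and 16% in Section 1.2. No planned analysis makes that comparison, and the benchmarks are not derived from those rates. The 31% was also adjudicated by central review, whereas response here is determined by the Investigator.

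Finally, the protocol leaves further analysis detail to an SAP. If a separate SAP settles the rule, what remains is to align Section 10.3.4 with it; nothing in the text reviewed does so. Glioblastoma is less exposed, because the RANO criteria in Table 13-2 already require CR and PR to be sustained for at least 4 weeks.

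**Conclusion.** The point holds as a conflict between two stated rules that the documents leave unreconciled. It reaches the ORR, DOR, the 5% and 15% benchmarks, the 3-of-25 guide and the interim count. Its one assumption-free consequence is that a single reclassified subject can move the lower 90% limit from 5.7% to 3.4%, across the 5% mark.

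The effect on error rates is conditional. If 5% is a confirmed rate and unconfirmed responses are counted, the chance of 3 or more in 25 rises from 12.7% to between 15.9% and 46.3% for assumed unconfirmed shares of 10% to 50%. If the benchmarks were set for unconfirmed responses, it stays at 12.7%. The direction under the first condition is certain, because unconfirmed responses can only add to the count; the size is not known. This should be corrected before the analysis, but it does not undermine the design.

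**What to change.** In Section 10.3.4:

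- Define a best overall response of CR or PR as one confirmed under Section 7.3, by a second consecutive qualifying assessment at least 4 weeks later.
- State that a response first recorded by End of Treatment counts if its confirming scan in follow-up qualifies and precedes progression and any new anticancer therapy.
- Apply the same definition to DOR in Section 10.3.5, to the 5% and 15% benchmarks and the 3-of-25 guide in Section 10.1, and to the interim count in Section 10.3.6.
- List unconfirmed CR and PR separately as supportive.

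The cost is a few sentences, since the confirmatory scans are already required. The reported ORR may be slightly lower. If the 15% target was in fact chosen with unconfirmed responses in mind, the sponsor should say so and restate the operating characteristics, because the 75% figure would then no longer apply to the confirmed count.
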